12.1.6. Notification of Post-Study SAEs

If an Investigator becomes aware of an SAE that may be attributable to the investigational product at any time after the end of the study, the medical monitor should be notified immediately (ie, within 24 hours).

All SAEs that occur within 30 days following the cessation of investigational product, whether or not they are related to the study, must be reported to the Sponsor within 24 hours by following the instructions provided in [Section 12.1.4.2](#).

12.1.7. Follow up of AEs and SAEs

All AEs must be followed during the course of the study until the AE resolves, is no longer of clinical concern, has stabilized or is otherwise explained, or the subject is lost to follow up.

AEs ongoing at the final visit that are deemed to be “possibly, probably, or definitely” related or of other clinical significance must be followed for as long as necessary to adequately evaluate the safety of the subject or until the event stabilizes, resolves, or is no longer of clinical concern. If resolved, a resolution date for the AE should be documented on the CRF. The Investigator must ensure that follow up includes any supplemental investigations indicated to elucidate the nature and/or causality of the AE. This may include additional laboratory tests or investigations, or consultation with other healthcare professionals, as considered clinically appropriate by the Investigator.

12.1.8. Pregnancy and Follow up

Pregnancies are not considered AEs in and of themselves; however, if a female study participant becomes pregnant while she is enrolled in the clinical study, she must discontinue investigational product and the Sponsor must be notified within 24 hours of the Investigator's learning of the pregnancy by completing the Pregnancy Notification Form and faxing or emailing to the Sponsor at [contact] or [contact].

Safety will be monitored and assessed by AEs/SAEs, medical history, physical examination, vital signs measurements, ECG results, and clinical laboratory assessments.

The subject may reinstate investigational product after delivery and cessation of breastfeeding (if applicable) at the discretion of the Investigator. Subjects whose pregnancy is terminated early (planned or unplanned) may be permitted to resume participation in the study if termination of the pregnancy is confirmed by a serum β -hCG test (see [Section 8.4.1](#)).

12.2. Other Safety Parameters

12.2.1. Medical History/Demographics

A complete medical history and PBC disease-specific history will be obtained from the subject at Screening. Smoking and alcohol consumption history and current habits will be recorded. Demographic characteristics (age, gender, race, and ethnicity) will be recorded.

12.2.2. Physical Examination

To assess for clinical findings, the Investigator or designee will perform a physical examination at the timepoints specified in the Schedule of Study Procedures ([Section 7.1.2](#)). A basic physical examination should be performed, including all body systems pertinent to the subject. Any clinically significant abnormality should be reported on the AE CRF page. Information about smoking and alcohol consumption habits will be collected at the same (follow-up) timepoints as the physical exam.

12.2.3. Vital Signs

Vital signs will be assessed at indicated visits: height, weight, oral temperature, sitting heart rate, respiratory rate, and sitting blood pressure. When taking heart rate, respiratory rate, and blood pressure readings, subjects should be seated quietly for a minimum of 3 minutes before the readings are taken.

12.2.4. Electrocardiogram

Standard 12-lead ECGs will be collected at the Screening visit and at EOT. The Investigator or designee will review the 12-lead ECG and findings will be recorded in the CRF as normal, abnormal but not clinically significant, or abnormal and clinically significant. Any clinically significant abnormality on ECGs should be reported on the AE CRF page.

Investigative sites must retain a copy of all 12-lead ECGs evaluated by the Investigator or designee. These ECGs must be clearly labeled with the subject's initials, Subject ID number, date, and time.

12.2.5. Dual Emission X-Ray Absorptiometry

A bone density assessment will be done using the DEXA scan.

12.2.5.1. Subject Questionnaires

Information about the subject's PBC disease history (ie, date of diagnosis, treatment history, pruritus history, signs and symptoms, and including smoking history) will be collected during Screening. At subsequent study visits (see [Section 7.1.2](#)), subjects will be asked to complete the following questionnaires; they may be asked to initial and date to document confirmation of their

responses, and the questionnaires should be filed in the subject's study records. These may require transcription to the CRF by study site staff.

- 5-D Pruritus Questionnaire: This is a questionnaire that has been validated in several different diseases. It assesses symptoms in terms of 5 domains: degree, duration, direction, disability and distribution [Elman 2010]
- Pruritus VAS: A Visual Analogue Scale (VAS) will also be used to assess pruritus in individual subjects

12.2.6. Laboratory Assessments

Subjects will be instructed to attend each of their study visits (except Screening) in a fasted state, and subjects should remain fasted until their blood samples have been collected. At each visit, the investigator or designee will verify that the subject has fasted for at least 8 hours and record fasting status in the source and CRF. If the subject reports having eaten (water is permitted) within 8 hours, the investigator or designee will document accordingly in the source and CRF and remind the subject that fasting is required prior to all study visits.

Blood samples for serum chemistry and hematology will be collected at every visit as detailed in the Schedule of Study Procedures (Section 7.1.2). The number and volume of samples to be collected at each visit will be detailed in the laboratory manual.

Full instructions concerning the number and type of samples to be collected at each visit, the required sample volumes, sample collection methods, sample processing, labeling, and shipping will be provided by the central clinical laboratory in a study specific laboratory manual. All necessary collection supplies will be provided by the central laboratory and will be appropriately assembled for the specific evaluations required at each visit.

All subjects with laboratory tests containing clinically significant abnormal values are to be followed regularly until the values return to normal ranges; until a valid reason, other than investigational product-related AE, is identified; or until further follow up is deemed medically unnecessary. Subjects testing positive for urine drug screen will be excluded from the study.

The list of laboratory analytes to be tested is shown in Table 4.

Table 4: List of Laboratory Analytes to be Tested

Laboratory Assessment	Analyte
Serum Chemistry	Albumin, blood urea nitrogen (BUN), creatinine, direct bilirubin, total bilirubin, aspartate aminotransferase [AST, SGOT], alanine aminotransferase [ALT, SGPT], ALP, GGT, electrolytes [calcium, chloride, potassium, sodium], glucose, total protein, and blood lipids (total cholesterol, LDL, HDL and very low density lipoprotein [VLDL] fractions and triglycerides[TG]), magnesium, phosphorus, bicarbonate, unconjugated (indirect) bilirubin, conjugated (direct) bilirubin, free fatty acids, thyroid hormones (T3, T4, TSH)

Laboratory Assessment	Analyte
Hematology	Hemoglobin, hematocrit, white blood count with differential, neutrophils, lymphocytes, monocytes, eosinophils, basophils, platelets, red blood cell count (including MCV, HBE [MCH], MCHC)
Coagulation	Prothrombin time (PT), partial thromboplastin time (PTT), international normalized ratio (INR)
Urinalysis	pH, specific gravity, total protein, glucose, ketones, bilirubin, blood, microscopic exam, urobilinogen, albumin, creatine, leucocytes, nitrates, albumin/creatinine ratio (if positive)
Biomarkers of Hepatic Fibrosis and/or Inflammation	IgM, C-reactive protein (CRP), TNF- α , FGF-19, CK-18, ELF, and others as determined during course of study
Measurement of Liver Fibrosis	Fibroscan
Bone Density Assessment	DEXA
Genetics	DNA including single-nucleotide polymorphisms (SNPs) that may be involved in PBC; RNA
Blood Sample for Future Analysis	PBC autoantibodies and other cytokines and interleukins TBD
Other	OCA (parent and conjugates [glyco and tauro]) and C4

The Investigator should manage subjects with clinically significant lipoprotein abnormalities using local standard of care procedures as appropriate after assessing the individual subject's total cardiovascular risk profile.

Urine-based β -hCG pregnancy tests will be performed in female subjects of childbearing potential per protocol specified visits. If a urine pregnancy test is positive, a serum pregnancy test must be performed to confirm the result. If positive, the Sponsor must be notified and the subject will be followed, as outlined in [Section 12.1.8](#) through pregnancy outcome.

MELD scores, Child-Pugh score and MRS will be calculated at quarterly visits based on serum chemistry and coagulation.

13. STATISTICAL METHODS

A statistical analysis plan (SAP), providing details about the specific planned analyses and hypothesis tests, will be prepared and approved by the Sponsor and its designees prior to study database lock, propensity score determination, and unblinding of the double-blind subject treatment assignments.

13.1. Efficacy Analysis

13.1.1. Analysis Populations

The following subject populations will be evaluated and used for presentation and analysis of the data:

- The Randomized Population will include all randomized subjects.
- The Intent-to-Treat (ITT) Population will include all randomized subjects who receive any amount of investigational product (OCA or placebo). The ITT Population will be the primary population used for efficacy analyses. Treatment assignment will be based on the randomized treatment.
- The Safety Population will include all subjects who received any amount of investigational product (placebo or OCA). The Safety Population will be the primary population used for safety analyses. Treatment assignment will be based on the treatment actually received.
- The PK population will include all OCA subjects who have at least one confirmed fasted analyzable sample. Subjects must have been fasting for approximately 8 hours prior to the visit and must not have any major protocol deviations that potentially affect exposure levels. The PK population will be used for OCA PK analyses.
- The Overall Historical Control Population will include subjects from the United Kingdom (UK) -PBC Group and Global PBC Study Group databases with demonstrated comparability to randomized subjects in this clinical study (747-302) with respect to both subject characteristics and disease progression.
- The UK-PBC Historical Control Population will include subjects from the UK-PBC Group databases with demonstrated comparability to randomized subjects in this clinical study (747-302) with respect to both subject characteristics and disease progression.
- The Global PBC Historical Control Population will include subjects from the Global PBC Study Group database with demonstrated comparability to randomized subjects in this clinical study (747-302) with respect to both subject characteristics and disease progression.

13.1.1.1. Comparability of Historical Controls

Utilization of both historical control/observational databases (UK-PBC and Global PBC Study Group), with more than 6000 subjects each, allow for a rigorous subject level meta-analysis. The historical databases include long-term follow up, detailed subject-level information such as baseline clinical characteristics, longitudinal liver biochemistry, and long-term outcomes, and span a broad range of subject characteristics that may influence disease (disease state, age, gender, and regional differences in standard of care). Historical controls from both databases will be chosen based on the same study inclusion/exclusion criteria where possible.

13.1.2. Determination of Sample Size

The following assumptions were used in sample size calculations:

- Exponential survival curves, placebo survival estimate of 0.5 at 8 years with a hazard ratio of 0.60, and total study duration of 8 years, allowing for 2 years accrual and 6 years of follow up.

- 5% of the subjects will have never been treated with UDCA; 95% of the subjects will have been on UDCA for at least 1 year.
- Subjects will be randomized in a 1:1 ratio to placebo or OCA.
- The 2 groups will be compared using a 2-sided log rank test at the 5% level of significance.

Based on the randomization ratio, significance level, and assumed hazard ratio, a total of 121 events (both groups combined) will provide 80% power to demonstrate a statistically significant difference between OCA and placebo on time to liver-related outcomes, including all-cause mortality.

In addition, based on the remaining assumptions stated above, it is estimated that approximately 350 subjects will be enrolled to attain 121 events.

13.1.2.1. Sample Size Re-Estimation Plan

Conducting a long-term outcomes study given the low disease prevalence, relatively slow disease progression, and ethical considerations, which in combination will impact recruitment and event rates, is inherently difficult. As stated in ICH E9, in long-term trials there is an opportunity to check the assumptions that underlay the original design and sample size calculations. The power stated above depends on the total number of events. Thus, the overall survival function can be estimated without unblinding.

Therefore, starting approximately 2 years after the first subject is randomized, the aggregate event rate and sample size based on recruitment and retention will be evaluated in a blinded manner quarterly. This evaluation will determine if any increases in number of subjects are required in order to obtain a total of 121 adjudicated events for the final analysis in the combined groups. Specifically, the pooled number of events will be available during the study in a blinded manner, without any knowledge of the comparative efficacy in the treatment groups. This method for evaluating the sample size does not inflate the type I error rate. Additional subjects may be enrolled as appropriate.

If after 4 years of accruing subjects, despite increases in the number of subjects, it is determined that at least an additional 2 years (ie, total study duration of at least 10 years) are needed to randomize sufficient subjects to achieve a total of 121 adjudicated events, all subjects enrolled from that point forward will receive open-label OCA. Previously randomized subjects will continue to be treated in a blinded manner with either OCA or matching placebo. If this modification is implemented, the alternative primary efficacy analysis is specified in [Section 13.1.9](#).

Any revised sample size or changes to treatment allocation will be justified and documented in a protocol amendment and in the CSR.

13.1.3. Primary Efficacy Analysis

The primary efficacy endpoint will be the time to first occurrence of one of the following post-randomization:

- Death (all-cause)

- Liver transplant
- MELD score ≥ 15
- Hospitalization (as defined by a stay of 24 hours or greater) for new onset or recurrence of:
 - Variceal bleed
 - Encephalopathy (as defined by a West Haven score of ≥ 2)
 - Spontaneous bacterial peritonitis (confirmed by diagnostic paracentesis)
- Uncontrolled ascites (diuretic resistant ascites requiring therapeutic paracentesis at a frequency of at least twice in a month)
- Hepatocellular carcinoma confirmed by 2 complimentary imaging modalities

The primary efficacy analysis will compare randomized OCA to randomized placebo with respect to the primary efficacy endpoint using the ITT population. Only adjudicated events will be included in analyses. The 2 treatment groups will be compared using the log rank test stratified by the randomization stratification factor. Kaplan-Meier (KM) estimates of the distribution of the time-to-event will be tabulated and graphed by treatment group. The tabulation will include the KM estimate of the medians and corresponding 95% confidence intervals (CIs), if the medians can be estimated. The number and percent of subjects censored and with events will be presented. The hazard ratio and 95% CI will be determined based on a Cox regression model stratified by randomization strata to estimate the magnitude of the effect.

13.1.4. Key Secondary Efficacy Analyses

The key secondary efficacy endpoints will compare OCA to placebo on the following:

- Time to first occurrence of MELD score ≥ 15
- Time to liver transplant or death (all-cause)
- Change from Baseline in total bilirubin at end of study
- Change from Baseline in ALP at end of study

The key secondary efficacy analyses will compare randomized OCA to randomized placebo in ITT population with respect to the key secondary efficacy endpoints. Only adjudicated events will be included in time-to-event analyses. The comparison (hypothesis testing) will be conducted as specified in [Section 13.1.11](#) in a sequential closed testing gate-keeping procedure, provided that the primary efficacy endpoint comparison is statistically significant in favor of the OCA treatment group. If the primary comparison is not statistically significant then comparison of the secondary endpoints will be considered as descriptive and exploratory. This procedure controls the study-wise type I error.

The 2 treatment groups will be compared using the same methodology as specified for the primary efficacy analysis ([Section 13.1.3](#)).

Analyses of change from Baseline to end of study in ALP and total bilirubin will be compared between treatment groups using analysis of covariance (ANCOVA) with change from Baseline

as the dependent variable including treatment group and randomization stratification factor as fixed effects and the Baseline values as a covariate. The same analysis will be carried out using percentage change from Baseline as the dependent variable.

Descriptive statistics of the laboratory values will be summarized by treatment group. The results, change from Baseline, and percentage change from Baseline values as well as estimates of least-square means, standard errors, and 95% CIs will be presented by treatment group. Estimates of the mean difference between treatment groups, the standard error of the difference, and 95% CI of the difference will be presented.

13.1.5. Additional Secondary Efficacy Analyses

The following time to event secondary efficacy analyses will compare randomized OCA versus randomized placebo using the ITT population:

- Time to each component of the primary efficacy endpoint (except MELD score ≥ 15 which is captured above)
- Time to liver-related death
- Time to liver-related death or liver transplant
- Time to liver-related death, liver transplant, or MELD score ≥ 15

The same analysis methodology as used for the primary efficacy analysis will be used for these secondary efficacy analyses. Similar endpoints, where available, will be analyzed to compare OCA to historical controls as described below in [Section 13.1.8](#).

Analyses of changes in liver biochemistry (GGT, ALT, AST, conjugated bilirubin, albumin, and INR) will be summarized and analyzed using the same methodology as specified in [Section 13.1.4](#) for the key secondary analyses of change in ALP and total bilirubin.

Analyses of changes in MELD score, Child-Pugh score, Mayo Risk Score (MRS), IgM, CRP, TNF- α , FGF-19, CK-18, C4, and ELF score will be summarized and analyzed using the Wilcoxon Rank Sum Test to compare treatment groups. The median differences and 95% CI of the median differences between treatment groups will be constructed using Hodges-Lehmann estimate. If the median differences between treatments are not symmetrical around the median, the Sign Test may be used.

13.1.6. Exploratory Efficacy Analyses

13.1.6.1. Responder Analyses

The percentage of subjects with a decrease in ALP of $\geq 15\%$ and $\geq 40\%$ from Baseline will be summarized by treatment group. In addition, the percentage of subjects with ALP \leq ULN will be summarized by treatment group.

The percentage of subjects that meet the criteria of a responder based on each of the definitions below will be summarized by treatment group. The response classification at baseline will also be included in the summary:

- ALP $\leq 3x$ ULN and AST $\leq 2x$ ULN and total bilirubin \leq ULN ([Corpechot 2008](#))
- ALP $\leq 1.5x$ ULN and AST $\leq 1.5x$ ULN and total bilirubin \leq ULN ([Corpechot 2011](#))

- ALP $\leq 1.67 \times$ ULN and total bilirubin \leq ULN (Momah 2012)
- Normal bilirubin (values \leq ULN) and normal albumin (values \geq lower limit of normal) (Kuiper 2009)
- ALP $\leq 1.76 \times$ ULN (Kumagi 2010)

Responder analyses will compare treatment groups using a Cochran–Mantel–Haenszel test stratified by the randomization stratification factor. Missing values will be considered as a non-responder.

13.1.7. Pharmacoeconomic and Health Outcomes Endpoints

Sufficient data will be collected on resource utilization and quality of life to undertake cost-effectiveness analyses that are relevant to the major countries taking part in this study. Resource utilization data on hospitalizations, healthcare provider visits, and medications will be combined with appropriate national unit costs to calculate a cost per patient per year in the study.

Quality of life data from patient-reported outcomes measures will be combined with survival data to calculate quality adjusted time in the study per patient. Cost-effectiveness analyses will report the incremental cost per major clinical outcome averted, liver-related death averted, life-year gained and quality-adjusted life year gained, including OCA as part of usual care versus usual care without OCA. Analyses will be conducted within the study and using a lifetime perspective. A separate economic analysis plan will be prepared and reported separately from this protocol.

13.1.8. Supportive Analysis

Per the International Conference on Harmonisation (ICH) E10 guidance, “where no obvious single optimal external control exists, it may be advisable to study multiple external controls”. In order to address the risks associated with the inclusion of a long-term placebo arm, supportive analyses of the primary endpoint will compare clinical outcomes in the OCA treatment arm to historical controls.

In an attempt to avoid the inherent biases with historical controls and to maintain the integrity of this comparison, one can invoke matching methods to optimize comparability and find a historical control that is “similar” to a participating subject. The historical database control should be as similar as possible to the study population and should have been exposed to a similar standard of care (see [Section 5.5.2.2](#)).

A propensity score can be used to reduce bias through matching, stratification, regression adjustment, or some combination. Propensity scores use information from a pool of patients who do not participate in the study (historical controls) to identify what would have happened to participating subjects in the absence of the treatment. By comparing how outcomes differ for treated subjects relative to historical controls, it is possible to estimate the effects of the treatment.

Although it might be relatively simple to assign a historical control based on a single observable characteristic, in practice, if the matching process is to successfully mitigate potential bias, it has to be done considering a full range of covariates across which the treatment and historical controls might differ. Although the results of using matching are conditional only on the

observed covariates, if one has the ability to measure many of the covariates that are believed to be related to the treatment assignment, then one can be fairly confident that approximately unbiased estimates for the treatment effect can be obtained. Both UK-PBC Group and the Global PBC Study Group formally collect numerous covariates that could be used for propensity score estimation including standard of care, eg, UDCA.

Historical controls will be chosen based on the same inclusion/exclusion criteria where possible.

Propensity scores will be estimated using the available covariates that predict receiving the treatment. Only covariates and not outcome variables will be included in the propensity score estimation. Therefore, there is no chance of biasing results in favor of one treatment.

The covariates and factors collected in the historical databases will be specified in the SAP.

Propensity scores will be estimated first through a logistic regression model with treatment group as the dependent variable and the above covariates/factors as independent variables. Then the stratum boundaries are determined based on the propensity score values for both groups (OCA population and control [historical and randomized placebo]) combined or in the OCA population or historical control group alone. Based on recommendations in the literature, quintiles of the estimated propensity score from the combined group will be used to determine the stratum boundary cut-offs for the different strata.

Outcome events collected in the historical database are: death (liver-related and all-cause), liver transplant, hepatocellular carcinoma, and other. Other is defined as cirrhosis or decompensation such as ascites, variceal bleed, and encephalopathy.

The propensity score quintile will be then be used as the stratification factor in the stratified log rank test to compare randomized OCA-treated subjects in the ITT population and historical controls (Overall Historical Control Population: both the UK-PBC Group and Global PBC Study Group databases) on the following outcomes:

- Time to death (all-cause)
- Time to liver-related death
- Time to liver transplant
- Time to liver transplant or death (all-cause)
- Time to liver transplant or liver-related death
- Time to hepatocellular carcinoma

KM estimates of the distribution of the time-to-event will be tabulated and graphed by treatment group. The tabulation will include the KM estimate of the medians and corresponding 95% CIs if the medians can be estimated. The number and percent of subjects censored and with events will be presented. The hazard ratio and 95% CI will be determined based on a Cox regression model stratified by randomization strata to estimate the magnitude of the effect.

Sensitivity analyses will be conducted limiting to the separate individual historical control databases, ie, UK-PBC Group and Global PBC Study Group. To evaluate the robustness of the propensity score estimations, additional algorithms and factors may be considered.

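### In the registry comparisons only the log rank test is stratified by propensity quintile; the curves, medians and event percentages are plain by-group displays that can differ even if OCA has no effect

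*Protocol*

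**What the plan says.** Section 13.1.8 compares randomized OCA subjects with patients from two registries. A propensity score is estimated by logistic regression and cut into quintiles, and the quintile stratifies the log rank test. For display, the section says "KM estimates of the distribution of the time-to-event will be tabulated and graphed by treatment group", adds Kaplan-Meier medians where they can be estimated, and says "The number and percent of subjects censored and with events will be presented". The hazard ratio comes from a Cox model stratified by randomization strata. These sentences closely follow the display text of the randomized primary analysis in 13.1.3.

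Section 13.1.9 repeats the same test, displays and Cox model for the alternative primary analysis. There, all OCA subjects, including any later open-label entrants, are compared with randomized placebo plus registry controls on transplant or death.

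On follow-up, the trial assumes "total study duration of 8 years, allowing for 2 years accrual and 6 years of follow up". For the registries, 13.1.1.1 says only "The historical databases include long-term follow up", with no length or distribution.

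The text of 13.1.8 and 13.1.9 is essentially the same in the original protocol and in Amendment 1. The extract of Amendment 1.1 ends before its Section 13.

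**The concern.** In a randomized comparison, plain by-group curves and percentages describe the contrast being tested. In a non-randomized one they need not. Section 13.1.8 itself says that historical controls carry inherent biases and that a full range of covariates must be considered, but only the test uses that adjustment. Two separate problems follow.

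- **Percent with events.** This rises with follow-up. If OCA subjects and controls are followed for different lengths of time, the percentages differ at equal risk.
- **Curves and medians.** Pooled by group, they carry whatever prognostic difference remains between OCA subjects and the selected controls.

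Readers take the size of a benefit from these outputs, which could disagree with the stratified test printed beside them. The hazard ratio does not settle the matter: randomization strata cover only UDCA use and bilirubin category. Under 13.1.9 the same displays would present a primary result.

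**Working it through.** **The plan's own figure.** Inputs from 13.1.2: "The 2 groups will be compared using a 2-sided log rank test at the 5% level of significance"; "Subjects will be randomized in a 1:1 ratio to placebo or OCA"; "Exponential survival curves, placebo survival estimate of 0.5 at 8 years with a hazard ratio of 0.60". Schoenfeld's formula gives 4 × (1.960 + 0.842)² / (ln 0.60)² = 4 × 7.849 / 0.2609 = 120.3, so 121 events, with power 80.2% at 121. This reproduces "a total of 121 events (both groups combined) will provide 80% power". The protocol gives no figure for the registry comparison, so everything below is illustration under stated assumptions, always with no OCA effect.

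**Percent with events.** With constant hazard h, a group followed for t years has 1 − exp(−ht) with events. For follow-up uniform from a to b years it has 1 − [exp(−ha) − exp(−hb)] / [h(b − a)]. The trial is taken as uniform over 6 to 8 years. The design's composite hazard is ln 2 / 8 = 0.0866 per year; the hazards 0.036 and 0.02 are assumed, because rates for the registry outcomes are not given. Registry follow-up is also assumed.

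| Hazard per year | Trial, 6–8 y | Registry 3 y | 5 y | 8 y | 10 y | 15 y |
|---|---|---|---|---|---|---|
| 0.0866 | 45.4% | 22.9% | 35.2% | 50.0% | 58.0% | 72.7% |
| 0.036 | 22.3% | 10.2% | 16.5% | 25.0% | 30.2% | 41.7% |
| 0.02 | 13.1% | 5.8% | 9.5% | 14.8% | 18.1% | 25.9% |

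Example, trial at 0.036: 1 − (0.8057 − 0.7498) / 0.072 = 22.3%. The sign depends on whether the registry was followed for less or more time than the trial.

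**Section 13.1.9.** Section 13.1.2.1 gives open-label OCA to everyone enrolled after the trigger, which comes after 4 years of accrual and implies a total duration of at least 10 years. Late entrants therefore join the OCA group only. Assume closure at year 10 and h = 0.036. Late entry in years 4–6 means 4–6 years of follow-up: 1 − (0.8659 − 0.8057) / 0.072 = 16.5%. Randomized entry in years 0–4 means 6–10 years: 1 − (0.8057 − 0.6977) / 0.144 = 25.0%. Late OCA entrants show fewer events than randomized placebo subjects at identical risk. Against the registry part of the control group, the direction is again unknown.

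**Kaplan-Meier and follow-up length.** Simulation at h = 0.0866 with equal risk, 200,000 subjects per group, follow-up uniform 6–8 years against uniform 0.5–12 years: 5-year Kaplan-Meier survival 0.649 and 0.650 (exact exp(−0.433) = 0.648), while percent with events is 45.4% and 39.3%. Follow-up moves the percent and leaves the curve alone, provided censoring is non-informative.

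**Kaplan-Meier and case mix.** Take five propensity strata with hazards 0.0866 × g^k, k = −2 to 2, and controls at 20% each. The assumed OCA mix is mild (14/17/20/23/26%) or moderate (8/13/20/26/33%). The within-stratum hazard ratio is 1.00.

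| Top-to-bottom hazard ratio (g⁴) | OCA mix | 7-year KM, OCA vs controls | Median (years) | Unstratified hazard ratio |
|---|---|---|---|---|
| 1.00 | either | 0.545 vs 0.545 | 8.0 vs 8.0 | 1.00 |
| 1.75 | mild | 0.529 vs 0.543 | 7.63 vs 7.95 | 1.04 |
| 1.75 | moderate | 0.514 vs 0.543 | 7.29 vs 7.95 | 1.09 |
| 2.86 | mild | 0.511 vs 0.537 | 7.24 vs 7.84 | 1.08 |
| 2.86 | moderate | 0.483 vs 0.537 | 6.66 vs 7.84 | 1.17 |

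Here OCA subjects were assumed to be the sicker group; a healthier OCA mix reverses the sign. The last column is the hazard ratio averaged over 7 years with no stratification. Stratifying by UDCA and bilirubin category could remove part of the excess; stratifying by quintile gives 1.00.

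**The case against.** Much of the case on the other side is sound.

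- **Follow-up and Kaplan-Meier.** A reader might infer that unequal follow-up distorts the curves and medians too. It does not, if censoring is non-informative.
- **Direction.** A reader might infer that registry percentages must be higher, which would flatter OCA. The protocol does not say how long registry patients were followed, and short registry follow-up gives the opposite sign. This stands.
- **Selection.** Controls are to meet the trial's eligibility criteria where possible (13.1.1.1, 13.1.8) and to show comparability in characteristics and disease progression (13.1.1). Remaining imbalance may be small. This stands as to size. It does not make unadjusted displays the right choice, because a propensity score is planned for use after that selection.
- **Medians.** At 3.6% per year the median is ln 2 / 0.036 = 19.3 years, beyond the planned trial follow-up, and medians are reported only where estimable. At such rates this part has no practical effect.
- **SAP territory.** Section 13 leaves detail to the SAP, and grouping by treatment does not forbid weighting. The SAP could indeed add weighted displays. But 13.1.8 names the outputs and gives the propensity quintile one use, so following it as written yields the unadjusted ones.
- **Standing of the comparison.** It is supportive (5.5.2.2), and 13.1.9 applies only after a conditional trigger that must be documented in an amendment. This limits the severity.
- **Role of the hazard ratio.** The protocol assigns effect size to the hazard ratio, not to percentages. That is true, but the hazard ratio is not stratified by the propensity quintile either.

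**Conclusion.** The point holds in a limited form. In 13.1.8 and 13.1.9 the only output that uses the propensity score is the log rank test. The curves, medians and percent with events are crude, and the hazard ratio is stratified on a different factor from the test. With no OCA effect, the crude percent can differ in either direction because of follow-up, and the curves and estimable medians can differ through residual prognostic imbalance alone.

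The documents do not support saying that the displays will differ, or by how much. The hazards 0.036 and 0.02, every registry follow-up length, the closure and entry times under 13.1.9 and the quintile mixes are assumptions. Under them, percentages differ by several to more than 20 points, and 7-year survival by 0 to about 5 points. Severity is low to moderate while the comparison is supportive, and higher if 13.1.9 becomes the primary analysis.

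**What to change.** In 13.1.8 and 13.1.9:

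1. Present Kaplan-Meier estimates for controls weighted or standardised to the propensity distribution of the OCA subjects, or shown by quintile, with the crude curve as a supplement.
2. Replace the percent with events, or accompany it, by Kaplan-Meier risk at a fixed time within the follow-up common to both groups, or by events per 100 patient-years. Under 13.1.9, choose a horizon that late OCA entrants also reach.
3. Stratify the Cox model by the propensity quintile used in the log rank test, so that the estimate and the test address the same comparison.

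The cost is a little programming and wording, with no new data. The displayed contrast may become smaller. The adjustment covers measured covariates only.
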